3.1 INCLUSION CRITERIA

Patients must meet all of the following inclusion criteria to be eligible for participation in this study:

1. Diagnosis of B-cell CLL or SLL, with diagnosis established according to IWCLL criteria and documented within medical records. Patients must not have received previous therapy for CLL/SLL
2. CLL/SLL that warrants treatment consistent with accepted IWCLL criteria for initiation of therapy. Any one of the following conditions constitutes CLL/SLL that warrants treatment:
 - a. Evidence of progressive marrow failure as manifested by the onset or worsening of anemia and/or thrombocytopenia, or
 - b. Massive (i.e., lower edge of spleen \geq 6 cm below the left costal margin), progressive, or symptomatic splenomegaly, or
 - c. Massive (i.e., \geq 10 cm in the longest diameter), progressive, or symptomatic lymphadenopathy, or
 - d. Progressive lymphocytosis in the absence of infection, with an increase in blood absolute lymphocyte count (ALC) \geq 50% over a 2-month period or lymphocyte doubling time of <6 months (as long as initial ALC was \geq 30,000/L), or
 - e. Autoimmune anemia and/or thrombocytopenia that is poorly responsive to corticosteroids or other standard therapy, or
 - f. Constitutional symptoms, defined as any one or more of the following disease-related symptoms or signs occurring in the absence of evidence of infection:
 - i. Unintentional weight loss of \geq 10% within the previous 6 months, or
 - ii. Significant fatigue (\geq Grade 2), or
 - iii. Fevers $>100.5^{\circ}\text{F}$ or 38.0°C for \geq 2 weeks, or
 - iv. Drenching night sweats for >1 month.
3. Adequate organ system function, defined as follows:
 - a. Absolute neutrophil count (ANC) \geq $0.5 \times 10^9/\text{L}$ and platelet count \geq $30 \times 10^9/\text{L}$
 - b. Total bilirubin \leq 2.5 times the upper limit of normal (ULN) unless due to Gilbert's disease
 - c. Alanine aminotransferase (ALT) and aspartate aminotransferase (AST) \leq 2.5 x ULN if no liver involvement or \leq 5 x the ULN if known liver involvement
 - d. Calculated creatinine clearance >30 mL/min (as calculated by the Cockcroft-Gault formula)
 - e. Patients with PT/INR or aPTT \leq 2xULN.
4. ECOG performance status \leq 2 unless related to CLL.
5. Male or female \geq 18 years of age.
6. Ability to swallow and retain oral medication.

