7 DOSE DELAYS/DOSE MODIFICATIONS

7.1 RITUXIMAB

No reduction in the dose of rituximab is permitted.

Supportive care should be considered for any patient who experiences Grade \geq 2 cytopenias, or Grade \geq 1 non-hematologic toxicities. Use of growth factors (such as G-CSF or pegylated G-CSF) is allowed, per ASCO guidelines (<http://jop.ascopubs.org/cgi/content/full/2/4/196>). A maximum four (4) week delay for recovery from toxicity is allowed for both rituximab and acalabrutinib (individually or together) to allow recovery of hematologic toxicities to \leq Grade 3 or non-hematologic toxicities to \leq Grade 2 or to baseline level. If the patient withdraws consent or has documented progression, an end of study visit should be completed.

Dose delay and/or modification guidance is for adverse events considered at least possibly related to the study drug. If cytopenias are deemed related to the underlying disease rather than study drug, dose modifications are not required, or are per investigator discretion. If a patient discontinues only one study drug, the patient may continue treatment with the other study drug per the protocol.

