7.2 STUDY DRUG MODIFICATIONS

- The actions should be taken for any Grade 4 toxicity or unmanageable Grade 3 toxicity. In addition, the actions in Table 7.2.1 should be taken when modification of acalabrutinib dose is recommended for specific treatment-related adverse events as listed in Table 7.2.2.
- If the dose of acalabrutinib is reduced, at the Investigator's discretion, the dose of acalabrutinib may be re-escalated after 2 cycles of a dose reduction in the absence of a recurrence of the toxicity that led to the reduction. Dose changes must be recorded in the study documentation.
- Dose modifications are for adverse events attributed to study treatment. Dose modifications are not required for adverse events unrelated to study treatment.
- Guidance for dose modifications in the event of drug interactions is provided in Table 6.2.1

TABLE 7.2.1: DOSE MODIFICATION ACTIONS FOR ACALABRUTINIB

Event Occurrence	Action
1 st -2 nd	May restart at original dose level (100 mg BID)
3 rd	Restart at 100 mg daily
4 th	Discontinue acalabrutinib

TABLE 7.2.2: STUDY DRUG MODIFICATIONS

	Rituximab	Acalabrutinib
NCI-CTCAE Grade		
Neutropenia		
Grade 3 neutropenia	Maintain current dose	Maintain current dose

	Rituximab	Acalabrutinib
Grade 4 neutropenia lasting >7 days or occurrence of neutropenic fever or infection	Delay rituximab until Grade ≤ 3 and/or neutropenic fever or infection is resolved; thereafter, resume at full dose. If delay is > 4 weeks, discontinue rituximab.	Hold acalabrutinib until recovery of Grade ≤ 3 or baseline. Follow dose modification actions in TABLE 7.2.1.
Thrombocytopenia		
Grade 3 thrombocytopenia	Maintain current dose	Maintain current dose
Grade 4 thrombocytopenia	Delay rituximab until Grade ≤ 3; thereafter resume at full dose. If delay is > 4 weeks, discontinue rituximab.	Hold acalabrutinib until recovery of Grade ≤ 3 or baseline. Follow dose modification actions in TABLE 7.2.1.
Diarrhea (non-infectious)		
Grade 1: increase of <4 stools per day over baseline	n/a	Provide antidiarrheal (eg, loperamide) and maintain current acalabrutinib dose level and schedule.
Grade 2: increase of 4-6 stools per day over baseline	n/a	Provide antidiarrheal (eg, loperamide). Withhold acalabrutinib until Grade ≤ 1. Resume acalabrutinib at current dose level. If rechallenge results in recurrence, may resume at initial or lower dose level at investigator discretion (if applicable). Consider addition of anti-inflammatory (eg, sulfasalazine, budesonide).

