Grade 3: increase of >7 stools per day over baseline	n/a	Provide antidiarrheal (eg, loperamide). Withhold acalabrutinib until Grade ≤ 1. Resume at lower dose level (if applicable). Consider addition of anti-inflammatory (eg, sulfasalazine, budesonide).
Grade 4: life-threatening	n/a	Provide antidiarrheal (eg, loperamide). Withhold acalabrutinib until Grade ≤ 1. May resume at lower dose level (if applicable) or discontinue acalabrutinib at investigator discretion. Consider addition of anti-inflammatory (eg, sulfasalazine, budesonide).
Immune related pneumonitis		
Grade 1	Withhold rituximab until resolved. Resume at full dose or if delay >4 weeks, discontinue rituximab	Maintain current dose. Consider pneumocystis prophylaxis
Grade ≥2	Discontinue rituximab, consider systemic corticosteroids and pneumocystis treatment.	Discontinue acalabrutinib, consider systemic corticosteroids and pneumocystis treatment.
Rash or injection site reaction		
Grade 1	Maintain current dose	Maintain current dose
Grade 2	Withhold rituximab until Grade ≤ 1. Resume at full dose or if delay >4 weeks, discontinue rituximab.	Maintain current dose

	Rituximab	Acalabrutinib
Grade 3 or 4	Withhold rituximab until Grade \leq 1. Resume at full dose or if delay >4 weeks, discontinue rituximab.	Withhold acalabrutinib until Grade \leq 1, consider systemic corticosteroids. Follow dose modification actions in TABLE 7.2.1.
All Other Non-Hematological Adverse Events		
Grade 3	Withhold rituximab until Grade \leq 1. Resume at full dose or if delay >4 weeks, discontinue rituximab.	Hold acalabrutinib until recovery of Grade \leq 1 or baseline. Follow dose modification actions in TABLE 7.2.1.
Grade 4	Discontinue rituximab.	Hold acalabrutinib until recovery of Grade \leq 1 or baseline. Follow dose modification actions in TABLE 7.2.1.

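### Section 7.1 sets non-hematologic recovery at Grade 2 or below or baseline, every numeric non-hematologic recovery cell in Table 7.2.2 sets Grade 1 or below, and no text says which governs

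*Combined protocol and SAP*

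**What the plan says.** Section 7.1 is headed Rituximab, but its delay rule names both drugs: "A maximum four (4) week delay for recovery from toxicity is allowed for both rituximab and acalabrutinib", individually or together. The same sentence gives two recovery levels: Grade 3 or below for hematologic toxicity, and "non-hematologic toxicities to \leq Grade 2 or to baseline level".

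Table 7.2.2 in Section 7.2 gives actions by event, grade and drug. Its non-hematologic recovery grade is always Grade 1 or below:

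- Rituximab, rash or injection site reaction Grade 2: "Withhold rituximab until Grade ≤ 1. Resume at full dose or if delay >4 weeks, discontinue rituximab". The rituximab cells for rash Grade 3 or 4 and for other non-hematologic Grade 3 events give the same instruction.
- Acalabrutinib, diarrhea Grade 2: "Withhold acalabrutinib until Grade ≤ 1. Resume acalabrutinib at current dose level". The Grade 3 and Grade 4 diarrhea cells use the same recovery grade.
- Acalabrutinib, rash Grade 3 or 4: "Withhold acalabrutinib until Grade \leq 1, consider systemic corticosteroids".
- Acalabrutinib, other non-hematologic Grade 3 and Grade 4: "Hold acalabrutinib until recovery of Grade \leq 1 or baseline".

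The introduction to Section 7.2 ties Table 7.2.1 to Table 7.2.2 and does not mention the level in Section 7.1. Section 7.2.1 (discontinuation) and Section 7.2.2 (ongoing treatment) give no recovery grade and do not rank Section 7.1 against the table.

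**The concern.** An investigator holding a drug for a related event has to know when it may be restarted, and the protocol gives two answers. If the event has settled at Grade 2, above the patient's baseline, the level in Section 7.1 is met and the level in the table is not. Rituximab dose reduction is not permitted, so the choice is full dose, continued hold or permanent stop. What is at stake is patient safety (restarting with Grade 2 toxicity still present) against loss of a study drug, and whether patients are handled alike. The exposure and dose-modification summaries in Section 9.4 would still record correctly what was given, but would reflect whichever rule was followed.

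**Working it through.** **Step 1. Set the two texts side by side.** These are all the non-hematologic cells of Table 7.2.2 with a numeric recovery grade:

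| Event and grade | Drug | Table: recovered at | Baseline alternative in table | Section 7.1: recovered at |
|---|---|---|---|---|
| Diarrhea 2 | acalabrutinib | ≤ 1 | no | ≤ 2 or baseline |
| Diarrhea 3 | acalabrutinib | ≤ 1 | no | ≤ 2 or baseline |
| Diarrhea 4 | acalabrutinib | ≤ 1 | no | ≤ 2 or baseline |
| Rash/injection site 2 | rituximab | ≤ 1 | no | ≤ 2 or baseline |
| Rash/injection site 3–4 | rituximab | ≤ 1 | no | ≤ 2 or baseline |
| Rash/injection site 3–4 | acalabrutinib | ≤ 1 | no | ≤ 2 or baseline |
| Other 3 | rituximab | ≤ 1 | no | ≤ 2 or baseline |
| Other 3 | acalabrutinib | ≤ 1 | yes | ≤ 2 or baseline |
| Other 4 | acalabrutinib | ≤ 1 | yes | ≤ 2 or baseline |

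The count is 3 rituximab + 6 acalabrutinib = 9 cells. All 9 require Grade 1 or below, and 9 − 2 = 7 lack a baseline alternative. The remaining non-hematologic cells maintain the dose, are marked not applicable, discontinue the drug, or (Grade 1 pneumonitis, rituximab) hold until resolution. The hematologic level, Grade 3 or below, agrees between text and table.

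**Step 2. Where the recovery grades lead to different actions.** Two of the nine cells are triggered by a Grade 2 event. The other 9 − 2 = 7 are triggered by Grade 3 or 4. There, an event that has improved to Grade 2, above baseline, meets Section 7.1 but not the table. The rituximab cells carry the same four-week limit as Section 7.1, so the two texts cannot be a restart level and a separate stop level. A related Grade 3 event still at Grade 2 at week 4 is recovered under one; under the other, rituximab is discontinued once the delay exceeds four weeks.

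**Step 3. Where the missing baseline alternative matters.** Of the 7 cells without it, the 3 diarrhea cells have no gap because those grades are already counted from baseline ("Grade 2: increase of 4-6 stools per day over baseline"). The Grade 2 rash cell has none either, because worsening from baseline Grade 2 moves the patient to the Grade 3–4 row. That leaves 7 − 3 − 1 = 3 cells: rituximab rash Grade 3–4, rituximab other Grade 3, and acalabrutinib rash Grade 3–4. Grade 2 fatigue can itself be the indication for treatment (Section 3.1), so a baseline Grade 2 condition is realistic. If it worsens to Grade 3 because of study drug and returns to Grade 2, the other Grade 3 row lets acalabrutinib restart but not rituximab.

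**Step 4. Size for one patient (illustration).** Planned rituximab doses are 6 cycles × 4 weeks × 2 = 48. Assume that held doses are not made up (the protocol gives no rule), that Grade 2 is reached at week w, and that Grade 1 is not reached by week 4. Doses depending on the reading = (48 − doses already given) − 2w.

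- Onset cycle 2 day 1 (8 given): w = 1, 40 − 2 = 38; w = 2, 40 − 4 = 36 (75% of 48); w = 3, 40 − 6 = 34.
- Onset cycle 1 day 8 (2 given), w = 2: 46 − 4 = 42 (87.5%).
- Onset cycle 6 day 1 (40 given), w = 2: 8 − 4 = 4.
- Onset cycle 2 day 1, Grade 2 at week 2 and Grade 1 at week 4: rituximab resumes under both readings, and (4 − 2) × 2 = 4 doses differ.

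**The case against.** The strongest reply is that Section 7.1 is permissive. It allows a delay, never orders a restart at Grade 2, and does not say what follows week 4. Someone who follows the table never breaches Section 7.1, and many would let the specific table override the general text. This stands in part: the section can be read as permitting an earlier restart but does not command one. It does not remove the problem. The sentence states recovery levels, its hematologic level matches the table's, and the precedence convention is not written down. Nor can Section 7.1 be ignored, since no acalabrutinib cell has a four-week limit; that limit appears only there.

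Four stronger readings are tempting and are not supported:

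- *That Section 7.1 would have new Grade 2 rash or Grade 2 diarrhea dosed through.* It contains no trigger for a hold. At onset the table's instruction to withhold stands uncontradicted, so doses withheld from onset of a Grade 2 event should not be counted as a product of the conflict.
- *That the baseline gap runs through all seven cells without the alternative.* It matters in three, and only for worsening attributed to study drug, because Sections 7.1 and 7.2 confine modification to related events. An investigator may also judge that fatigue back at its pre-treatment grade is disease only, which narrows the gap further.
- *That most of a patient's rituximab is typically at stake.* The larger dose counts belong to chosen trajectories; late onset or recovery to Grade 1 by week 4 brings the difference down to 4 doses.
- *That the primary analysis is compromised.* The treated population, the complete response denominator (Section 9.6), the sample size and the exact interval do not depend on this wording.

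The trial is single-center, so there is no divergence between sites. Investigators at one center can still differ.

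**Conclusion.** The inconsistency is real: 9 of 9 numeric non-hematologic recovery cells are stricter than Section 7.1, with no stated precedence. It affects drug-related events that caused a hold and improved only to Grade 2 above baseline and, in three cells, drug-related worsening of a baseline Grade 2 condition. For those patients the reading chosen decides between restart and continued hold and, for rituximab after four weeks, between treatment and permanent discontinuation. The documents do not give the frequency of such events, so the number of patients affected cannot be computed. The 4 to 42 of 48 doses are illustrations, not bounds, and rest on the assumptions stated with them. This is a modest, safety-relevant wording error that should be corrected. It does not weaken the statistical design.

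**What to change.** 1. In Section 7.1, change the non-hematologic recovery level to *Grade 1 or below, or baseline*.
2. In Table 7.2.2, add *or baseline* to three cells: rituximab rash Grade 3 or 4, rituximab other non-hematologic Grade 3, and acalabrutinib rash Grade 3 or 4.
3. Add a sentence: *The event-specific rows of Table 7.2.2 govern the recovery grade; the four-week maximum delay in Section 7.1 continues to apply to both drugs.* This also keeps the separate requirement that Grade 1 pneumonitis resolve before rituximab resumes.

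Do not add a clause making Section 7.2.1 override the table. That section lists life-threatening treatment-related reactions, and Appendix 2 labels Grade 4 hematologic toxicity life-threatening. An override could therefore turn the hold-and-resume rows for Grade 4 neutropenia and thrombocytopenia, and the acalabrutinib row for other Grade 4 events, into permanent discontinuation. The disagreement between the Grade 4 diarrhea row and Section 7.2.1 is a separate point.

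The cost is a wording amendment with IRB review, and no additional data or patients. The downside is that some patients with residual Grade 2 toxicity will be held longer or will lose rituximab.

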7.2 STUDY DRUG MODIFICATIONS

- The actions should be taken for any Grade 4 toxicity or unmanageable Grade 3 toxicity. In addition, the actions in Table 7.2.1 should be taken when modification of acalabrutinib dose is recommended for specific treatment-related adverse events as listed in Table 7.2.2.
- If the dose of acalabrutinib is reduced, at the Investigator's discretion, the dose of acalabrutinib may be re-escalated after 2 cycles of a dose reduction in the absence of a recurrence of the toxicity that led to the reduction. Dose changes must be recorded in the study documentation.
- Dose modifications are for adverse events attributed to study treatment. Dose modifications are not required for adverse events unrelated to study treatment.
- Guidance for dose modifications in the event of drug interactions is provided in Table 6.2.1

TABLE 7.2.1: DOSE MODIFICATION ACTIONS FOR ACALABRUTINIB

Event Occurrence	Action
1 st -2 nd	May restart at original dose level (100 mg BID)
3 rd	Restart at 100 mg daily
4 th	Discontinue acalabrutinib

TABLE 7.2.2: STUDY DRUG MODIFICATIONS

	Rituximab	Acalabrutinib
NCI-CTCAE Grade		
Neutropenia		
Grade 3 neutropenia	Maintain current dose	Maintain current dose

	Rituximab	Acalabrutinib
Grade 4 neutropenia lasting >7 days or occurrence of neutropenic fever or infection	Delay rituximab until Grade ≤ 3 and/or neutropenic fever or infection is resolved; thereafter, resume at full dose. If delay is > 4 weeks, discontinue rituximab.	Hold acalabrutinib until recovery of Grade ≤ 3 or baseline. Follow dose modification actions in TABLE 7.2.1.
Thrombocytopenia		
Grade 3 thrombocytopenia	Maintain current dose	Maintain current dose
Grade 4 thrombocytopenia	Delay rituximab until Grade ≤ 3; thereafter resume at full dose. If delay is > 4 weeks, discontinue rituximab.	Hold acalabrutinib until recovery of Grade ≤ 3 or baseline. Follow dose modification actions in TABLE 7.2.1.
Diarrhea (non-infectious)		
Grade 1: increase of <4 stools per day over baseline	n/a	Provide antidiarrheal (eg, loperamide) and maintain current acalabrutinib dose level and schedule.
Grade 2: increase of 4-6 stools per day over baseline	n/a	Provide antidiarrheal (eg, loperamide). Withhold acalabrutinib until Grade ≤ 1. Resume acalabrutinib at current dose level. If rechallenge results in recurrence, may resume at initial or lower dose level at investigator discretion (if applicable). Consider addition of anti-inflammatory (eg, sulfasalazine, budesonide).
Grade 3: increase of >7 stools per day over baseline	n/a	Provide antidiarrheal (eg, loperamide). Withhold acalabrutinib until Grade ≤ 1. Resume at lower dose level (if applicable). Consider addition of anti-inflammatory (eg, sulfasalazine, budesonide).
Grade 4: life-threatening	n/a	Provide antidiarrheal (eg, loperamide). Withhold acalabrutinib until Grade ≤ 1. May resume at lower dose level (if applicable) or discontinue acalabrutinib at investigator discretion. Consider addition of anti-inflammatory (eg, sulfasalazine, budesonide).
Immune related pneumonitis		
Grade 1	Withhold rituximab until resolved. Resume at full dose or if delay >4 weeks, discontinue rituximab	Maintain current dose. Consider pneumocystis prophylaxis
Grade ≥2	Discontinue rituximab, consider systemic corticosteroids and pneumocystis treatment.	Discontinue acalabrutinib, consider systemic corticosteroids and pneumocystis treatment.
Rash or injection site reaction		
Grade 1	Maintain current dose	Maintain current dose
Grade 2	Withhold rituximab until Grade ≤ 1. Resume at full dose or if delay >4 weeks, discontinue rituximab.	Maintain current dose

	Rituximab	Acalabrutinib
Grade 3 or 4	Withhold rituximab until Grade \leq 1. Resume at full dose or if delay >4 weeks, discontinue rituximab.	Withhold acalabrutinib until Grade \leq 1, consider systemic corticosteroids. Follow dose modification actions in TABLE 7.2.1.
All Other Non-Hematological Adverse Events		
Grade 3	Withhold rituximab until Grade \leq 1. Resume at full dose or if delay >4 weeks, discontinue rituximab.	Hold acalabrutinib until recovery of Grade \leq 1 or baseline. Follow dose modification actions in TABLE 7.2.1.
Grade 4	Discontinue rituximab.	Hold acalabrutinib until recovery of Grade \leq 1 or baseline. Follow dose modification actions in TABLE 7.2.1.

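### Section 7.2 and its two tables conflict on when brief Grade 4 neutropenia counts toward stopping acalabrutinib, and on the restart dose after Grade 3 diarrhea

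*Combined protocol and SAP*

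**What the plan says.** Section 7.2 gives two routes to an acalabrutinib action. The first is general: "The actions should be taken for any Grade 4 toxicity or unmanageable Grade 3 toxicity". The second is introduced as an addition to it: "the actions in Table 7.2.1 should be taken when modification of acalabrutinib dose is recommended for specific treatment-related adverse events", meaning those listed in Table 7.2.2.

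Table 7.2.1 is a ladder indexed by occurrence:
- 1st and 2nd: "May restart at original dose level (100 mg BID")
- 3rd: "Restart at 100 mg daily"
- 4th: "Discontinue acalabrutinib"

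Table 7.2.2 then gives event-specific rows. Its neutropenia row that leads to a hold and to Table 7.2.1 is limited to "Grade 4 neutropenia lasting >7 days or occurrence of neutropenic fever or infection". Its Grade 3 neutropenia and Grade 3 thrombocytopenia rows leave both drugs unchanged, with no exception for unmanageable cases. Its Grade 3 diarrhea row says "Resume at lower dose level (if applicable"), with no occurrence count and no reference to Table 7.2.1.

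The separate list of discontinuation criteria in Section 7.2.1 (not to be confused with Table 7.2.1) includes treatment-related Grade 4 diarrhea or colitis.

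**The concern.** The ladder ends in permanent discontinuation at the 4th occurrence, so the protocol has to be clear about which events count and where dosing restarts. On brief Grade 4 neutropenia, unmanageable Grade 3 cytopenias and Grade 3 diarrhea, the bullet and the tables give different answers for the same event.

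Two things are at stake. Patients with the same toxicity may be continued, reduced or stopped depending on the passage consulted. And the tables of dose modifications by type and cycle (Section 9.4) and of reasons for discontinuation (Section 9.2) would mix drug tolerability with choice of rule, in a trial where safety is a secondary objective.

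**Working it through.** The plan gives no figure on this point, so the check is to run the same events through each rule. Assumption: the unnamed actions in the opening bullet are those of Table 7.2.1, the only ladder in the section. Only events attributed to study treatment are considered, as Sections 7.1 and 7.2 require.

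**Step 1. Four Grade 4 neutropenia episodes, each of 7 days or less, without fever or infection**

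| Episode | Opening bullet, then Table 7.2.1 | Table 7.2.2 |
|---|---|---|
| 1 | may restart at 100 mg BID | no row applies |
| 2 | may restart at 100 mg BID | no row applies |
| 3 | 100 mg daily | no row applies |
| 4 | discontinue | no row applies |

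Under the bullet all four count and the patient comes off acalabrutinib. Under the table none counts and the ladder never starts.

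**Step 2. Unmanageable Grade 3 neutropenia or thrombocytopenia**

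The bullet calls for action. Table 7.2.2 says to leave the dose alone. Here both passages speak directly to the event and differ.

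**Step 3. Can the duration condition be seen from scheduled visits?**

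Table 5.1 schedules hematology several times in cycle 1 (day 1, day 3, 4 or 5, day 8, day 15). From cycle 2 to cycle 12 it is scheduled on day 1 only, so scheduled counts are nominally 28 days apart. A Grade 4 count at one visit and a recovered count at the next fit an episode shorter or longer than 7 days. Scheduled visits alone do not settle it; an unscheduled count could.

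**Step 4. Four Grade 3 diarrhea events**

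| Event | Table 7.2.1, applied through the Section 7.2 text | Diarrhea row of Table 7.2.2 |
|---|---|---|
| 1 | may restart at 100 mg BID | lower dose level |
| 2 | may restart at 100 mg BID | lower dose level |
| 3 | 100 mg daily | lower dose level |
| 4 | discontinue | lower dose level, no stopping point stated |

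Diarrhea is listed in Table 7.2.2, so the text sends it to Table 7.2.1, while its own row carries a different instruction.

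**Step 5. One treatment-related Grade 4 diarrhea**

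Table 7.2.1 permits restart at 100 mg BID. The Table 7.2.2 row permits resumption at a lower level or discontinuation at the investigator's discretion. Section 7.2.1 lists the event as warranting discontinuation. That is three answers to one event.

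**Step 6. Effect on the design figures**

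None. The precision statement in Section 9.1 (20% CR, 40 subjects, 95% interval 9.1% to 35.6%) does not depend on these rules. An exact interval for 8/40 gives 9.05% to 35.65%, as stated.

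**The case against.** **The rows can be harmonized.** The bullet and Table 7.2.2 are joined as an addition, so the bullet could supply the rule for brief Grade 4 neutropenia where the table has no row. That is a possible reading, but the 7-day limit in the neutropenia row would then have no effect on acalabrutinib, and the Grade 3 cytopenia conflict in Step 2 would remain.

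**The diarrhea row is a specific override.** Restart at the original dose in Table 7.2.1 is permissive, and the diarrhea rows, unlike the Grade 4 hematologic, severe rash and other non-hematologic rows, do not cite that table. Reading them as overrides is natural. This narrows the restart-dose problem to diarrhea but does not remove it: no precedence is stated, and nothing says whether a diarrhea event counts toward the ladder.

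**Unscheduled counts are available.** Table 5.1 lists required assessments and does not bar others, and holding a drug until recovery implies repeat counts. This stands, so the duration condition is not unworkable.

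A reader might also infer three stronger points that the documents do not support.

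- *That the Grade 3 rash row and the Grade 3 row under "All Other Non-Hematological Adverse Events" contradict the word unmanageable in the bullet.* They do not: the bullet's second sentence adds the Table 7.2.2 events to the first.
- *That 4 to 10 of 40 patients are affected.* This comes from 10.4% × 40 = 4.2 and 24.4% × 40 = 9.8. Those are Grade 3 or higher neutropenia rates from acalabrutinib monotherapy and from a combination with obinutuzumab. The Grade 4 share is not given, and the share that is brief and uncomplicated is smaller still. The quoted diarrhea rates (40.4% and 62.2%) are for any grade. Diarrhea is absent from both lists of most frequent Grade 3 or higher events, which end at 3.1% and 6.7%. If those lists are complete down to their last entry, that is at most 3.1% × 40 = 1.2 to 6.7% × 40 = 2.7 patients.
- *That each patient taken off acalabrutinib costs 1/40 = 2.5 points of the CR rate.* Section 9.6 uses best overall response among all treated patients, so a response recorded before stopping still counts, and Sections 4.3 and 8 keep such patients in follow-up for progression. Even if stopping ruled out CR, the expected loss at the anticipated 20% would be 0.20 × 2.5 = 0.5 points per patient.

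**Conclusion.** The point holds in two places: the trigger for cytopenias (brief uncomplicated Grade 4 neutropenia, and unmanageable Grade 3 neutropenia or thrombocytopenia), and the restart rule for Grade 3 diarrhea. In each, following a stated rule exactly can lead to different dosing, and on repetition to discontinuation under one reading only. The conflict between Table 7.2.2 and Section 7.2.1 on Grade 4 diarrhea belongs to the same problem.

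The conclusion assumes that the bullet's actions are those of Table 7.2.1 and that no precedence rule exists elsewhere; the protocol states none. The number of patients affected cannot be derived, and reaching a 4th occurrence may be uncommon. The effect on the CR rate cannot be quantified. The matter should be corrected for consistent patient management and readable exposure and discontinuation tables; the primary analysis is not in question.

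**What to change.** In one protocol amendment:

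1. Reconcile the opening bullet of Section 7.2, Table 7.2.1 and the neutropenia, thrombocytopenia and diarrhea rows of Table 7.2.2 so that a single list defines which events count as an occurrence. State also whether occurrences are counted per toxicity or across toxicities, which Table 7.2.1 does not say.
2. State whether diarrhea follows Table 7.2.1 or its own row, and whether a diarrhea event counts toward the ladder.
3. Reconcile these with the discontinuation criteria in Section 7.2.1, in particular for Grade 4 diarrhea.
4. If a duration condition for neutropenia is kept, say which count establishes it.
5. For patients already treated, record which rule was applied to each modification, so that the tables under Sections 9.2 and 9.4 can be interpreted.

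Which doses and thresholds to adopt is for the investigators. The cost is wording, plus at most a repeat blood count in patients with Grade 4 neutropenia.

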7.2.1 DISCONTINUATION CRITERIA

Regardless of the inciting agent, the following warrant treatment discontinuation:

- Treatment related adverse reactions that are life-threatening.
- Treatment related diarrhea or colitis, grade 4; also administer high-dose systemic corticosteroids.
- Infusion-related reaction, grade 4.
- Treatment related immune-related Pneumonitis, Grade 2 or higher; also administer high-dose systemic corticosteroids.

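### Table 7.2.2 lets acalabrutinib resume after treatment-related Grade 4 diarrhea, while Section 7.2.1 says that event warrants stopping treatment and giving high-dose systemic corticosteroids

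*Combined protocol and SAP*

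**What the plan says.** Section 7.2 applies the dose modifications in Table 7.2.2 to treatment-related events. The table's diarrhea block covers non-infectious diarrhea, and its last row is labeled "Grade 4: life-threatening". For acalabrutinib that row gives an antidiarrheal, a hold until Grade 1 or lower, and then: "May resume at lower dose level (if applicable) or discontinue acalabrutinib at investigator discretion". An added anti-inflammatory (sulfasalazine or budesonide are the examples) is to be considered. The rituximab column is n/a.

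Section 7.2.1, Discontinuation Criteria (not to be confused with Table 7.2.1, the acalabrutinib dose ladder), opens: "Regardless of the inciting agent, the following warrant treatment discontinuation". Its list includes "Treatment related diarrhea or colitis, grade 4; also administer high-dose systemic corticosteroids" and, separately, "Treatment related adverse reactions that are life-threatening".

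Neither place refers to the other, and no sentence gives one precedence.

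**The concern.** For a toxicity that the table itself labels life-threatening, one part of the protocol permits a restart and another calls for a stop with high-dose steroids. An investigator who opens the dose table, which is where one would look during an event, finds permission to resume and no mention of high-dose systemic corticosteroids. Another who opens Section 7.2.1 finds the opposite. The less cautious action is the one written in the table. Handling could therefore differ between patients with the same event, and exposure after it could too.

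**Working it through.** No formula or stated figure is involved in the conflict, so the check sets the two texts side by side.

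| | Table 7.2.2, Grade 4 diarrhea | Section 7.2.1 |
|---|---|---|
| Event covered | Treatment-related, non-infectious | Treatment-related diarrhea or colitis, Grade 4 |
| Acalabrutinib | Hold, then lower dose or stop, by discretion | Discontinue |
| Rituximab | n/a | Treatment discontinued; which drugs is not stated |
| Medicines | Loperamide; consider sulfasalazine or budesonide | High-dose systemic corticosteroids |
| Precedence | None stated | None stated |

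Can the two be reconciled?

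1. *By attribution?* No. Both are limited to treatment-related events.
2. *By grade?* No. Both name Grade 4.
3. *By the specific rule prevailing over the general?* No. Both name diarrhea.
4. *By the table's other rows?* The pneumonitis row at Grade 2 or higher stops both drugs, in line with Section 7.2.1. The table can therefore carry a stop instruction, and the diarrhea row does not.

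Colitis has no row of its own. It falls either under diarrhea or under All Other Non-Hematological Adverse Events at Grade 4. The first allows a lower-dose restart of acalabrutinib; the second sends acalabrutinib to Table 7.2.1, which may restart it at 100 mg BID after a first or second event. Section 7.2.1 names Grade 4 colitis, so the mismatch arises under either row.

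What stopping treatment covers is also open. Section 7.1 lets a patient who discontinues one drug continue the other, and Section 7.2.1 does not say whether both drugs stop.

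*How often?* Section 1.4 reports diarrhea of any grade in 40.4% on acalabrutinib monotherapy and 62.2% with obinutuzumab. Diarrhea is absent from both lists of the most frequent events of Grade 3 or worse. The lowest entries on those lists are 3.1% (monotherapy) and 3 of 45, or 6.7% (with obinutuzumab). Assume that diarrhea of Grade 3 or worse is no more frequent than the lowest listed entry, and that those populations are a fair guide to this one. Then, for 40 patients:

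- 3.1% × 40 = 1.24
- 3/45 × 40 = 2.67

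This is an assumed ceiling for Grade 3 or worse. The documents give no Grade 4 rate, so the number of patients actually exposed to the conflict is lower by an unknown amount.

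**The case against.** The best defense is that the texts can be followed together. To warrant a stop is softer than to require one. The table offers discontinuation as an option, so an investigator who stops and gives steroids satisfies both. Section 7.2.1 reads naturally as a limit on the table's discretion, Section 4.3 lists severe toxicity as a reason to discontinue, and Section 7.2.2 makes continuing conditional on no intolerable toxicity. The trial has a single center, which limits divergence. All of this stands as far as it goes, and restarting without steroids would indeed depart from Section 7.2.1. But the table still expressly authorizes that restart, the steroid instruction is missing from its row, and none of these sections states an order of precedence.

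A reader might infer three stronger points, which the documents do not support.

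- *That every Grade 4 row conflicts.* The "Rash or injection site reaction" row lets rituximab resume after Grade 3 or 4 ("Resume at full dose or if delay >4 weeks, discontinue rituximab"), and acalabrutinib is sent to the ladder there and under All Other at Grade 4. This conflicts with the life-threatening criterion only if Grade 4 always means life-threatening. The diarrhea label and the Section 10.1 grade definition (given for events outside CTCAE) lean that way. Section 10.2 separates the two: a Grade 3 or 4 event need not be serious, and life-threatening means immediate risk of death. The separate Section 7.2.1 entry for Grade 4 infusion-related reaction would also be redundant under that equation. And because Appendix 2 calls Grade 4 hematologic toxicity life-threatening, the equation would turn every Grade 4 cytopenia into a stop, against the table's own cytopenia rows.
- *That the ladder allows up to three restarts after Grade 4 diarrhea.* That cell does not cite Table 7.2.1. It sets its own action: a lower dose or a stop.
- *That a Grade 3 injection site reaction wrongly holds oral acalabrutinib.* The row does say so literally, and Section 7.2 refers to study treatment as a whole. But Section 7.1 ties the guidance to events at least possibly related to the study drug and lets the other drug continue. Rash is a listed acalabrutinib risk, so a shared row is defensible.

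**Conclusion.** The conflict holds for treatment-related Grade 4 diarrhea, and on the same footing for Grade 4 colitis, which the table does not list. It rests on the text alone and needs no inference about what Grade 4 means. It should be corrected because following the table as written gives the less safe action for an event that the protocol elsewhere says warrants stopping. The size is small in patient numbers: fewer than the assumed ceiling of about 1.2 to 2.7 per 40, which itself counts Grade 3 or worse. The sample size, the confidence interval and the primary complete response analysis are not shown to be affected.

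**What to change.** Either of two changes would do.

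1. Change the Grade 4 diarrhea entry in Table 7.2.2 to discontinue treatment and give high-dose systemic corticosteroids, and widen the row to name colitis.
2. Add one sentence that Section 7.2.1 overrides Table 7.2.2 for the events it lists, including Grade 4 colitis.

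With either, state in Section 7.2.1 whether both drugs stop. That also settles Grade 4 infusion-related reaction, where the All Other row stops rituximab but allows acalabrutinib to restart.

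If the override sentence is used, add that life-threatening in Section 7.2.1 means immediate risk of death, as in Section 10.2. Grade 4 cytopenias, and other Grade 4 events that are not immediately life-threatening and not named in Section 7.2.1, then stay under their table rows.

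The cost is a few words in a protocol amendment, with the IRB submission that Section 11.1 requires. No new data are collected and no analysis changes.
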